7.13 Proton APBI

In situations where patients present to a radiation oncologist pre-operatively, if they meet study eligibility criteria they may be consented at that time for proton APBI. After lumpectomy and axillary staging, at their postoperative visit in the radiation oncology department (generally 1-6 weeks following surgery) final pathology and eligibility will be confirmed. Consent may also be obtained for

proton APBI at that time if it was not provided preoperatively or if the patient is consulting with the treating radiation oncologist for the first time. Patient must begin treatment \leq 10 weeks after their last surgery.

Radiation Details:

Localization, Simulation, Immobilization: Prior to the treatment planning CT scan patients must be immobilized in the supine position in an arm up or down position at the discretion of the treating radiation oncologist. Slice thickness should be 0.3 cm or less.

Treatment Planning/Delivery: Any combination of at least 2 proton beams may be used provided that the dosimetric requirements of the planning target volume (PTV) and homogeneity are met. Proton APBI should begin within 10 weeks of lumpectomy or re-excision of margins.

Image Guidance for IGRT: Orthogonal kilovoltage (KV) images matched to fiducial markers placed at the time of lumpectomy should be performed to ensure reproducibility of setup prior to initiation of each treatment.

Definition of Target Volumes: The radiation oncologist will identify and outline the tumor bed by noting contrasting areas of density and architectural distortion as well as the presence of clips or fiducials in the breast. Information from the surgical report, mammography, MRI and other available imaging should be taken into account when available. A margin of 1cm will then be added to the tumor bed in order to create the CTV. The CTV will be limited, however, to 5mm from the skin surface and by the posterior breast tissue extent (chest wall and pectoralis muscles are not to be included). The proton PTV expansion will be defined initially as a 5mm expansion of the CTV to compensate for variability of set-up and any motion of the breast during treatment but will be expanded or contracted as necessary to maintain a 3.0%/3mm robustness such that the CTV coverage of 95% of the volume gets at least 95% of the dose. The border of this proton PTV will be limited to within 5mm below the skin surface and posteriorly to the anterior surface of the ribs. It is preferred that the PTV does not exceed 30% of the breast volume. If it does, a patient could potentially wait for 1-3 weeks until the seroma decreases in size and another planning session is performed.

Dose Prescription to PTV: The prescribed radiotherapy dose will be 21.9 Gy in 7.3 daily fractions (total of 3 fractions). Radiotherapy should aim to be delivered on three consecutive work days. Per protocol \geq 95% of the target volume CTV should be covered by \geq 95% of the prescribed dose of 21.9Gy.

Definition and Dose Limitations of Normal Tissues/Organs at Risk (OARs): The following normal tissue structures should be contoured for all patients by the physician: uninvolved normal breast, ipsilateral lung, contralateral lung, heart and skin.

Uninvolved ipsilateral normal breast: Includes the glandular breast tissue visualized by CT and the consensus definitions regarding “breast” from the RTOG breast atlas. The structure should be limited to 5mm from the skin surface to minimize inaccuracy of dose calculation at the skin surface. Per

protocol <35% (variation acceptable <50%) of the whole breast reference volume should receive $\geq 50\%$ of the prescribed dose and <20% (variation acceptable <30%) of the whole breast reference volume should receive the prescribed dose.

Ipsilateral lung: May be contoured with auto-segmentation with manual verification. The volume receiving 20Gy should not exceed 2%. The volume receiving 10Gy should not exceed 5%. The volume receiving 5Gy should not exceed 10%.

Contralateral lung: The volume receiving 20Gy should be 0. The volume receiving 10Gy should be <1%. The volume receiving 5Gy should be <2%.

Heart: The heart should be contoured beginning just inferior to the level in which the pulmonary trunk branches into the left and right pulmonary arteries (PA) and extending to its most inferior extent near the diaphragm. Contouring along the pericardium itself, when visible, is appropriate. The esophagus, ascending and descending aorta, and inferior vena cava should be excluded. The volume of heart receiving 1.5Gy should be less than 40%.

Skin: The maximum dose at the skin surface, defined as the most superficial 3mm of the body surface, should be reduced to as low as achievable while satisfying the other dose parameters but should not exceed 100% of prescription. If this constraint cannot be met than a different APBI technique can be considered on study.

8.0 Radiotherapy Dose Modifications Based on Adverse Events

8.1 Compliance Criteria

Treatment breaks must be clearly indicated in the treatment record along with the reason(s) for the treatment break(s). Radiation breaks, if necessary, should not exceed one treatment day. Radiation breaks should be allowed only for resolution of severe acute toxicity and/or for intercurrent illness and not for social or logistical reasons.

8.2 Radiation Therapy Adverse Events

The descriptions and grading scales found in the revised NCI Common Terminology Criteria for Adverse Events (CTCAE), version 4 will be utilized for grading all adverse events. All appropriate treatment areas should have access to a copy of the CTCAE, v. 4. A copy of the CTCAE, v. 4 can be downloaded from the CTEP web site
 (██████████).

EVENTS EXPECTED

Erythema, dry desquamation, hyper or hypopigmentation are anticipated to occur commonly. Some patients may develop moist desquamation, which usually heals within 2-3 weeks. Mild swelling of the breast or mild breast pain are also likely side effects of treatment. It is not anticipated that treatment breaks should be needed, as severe acute toxicities are extremely rare.

Transient, persistent, and occasionally symptomatic seroma formation can occur and will be monitored for during treatment and at follow-up. Telangiectasia, and chronic changes in pigmentation can also commonly be seen, as can soft tissue fibrosis.

Infection is less likely, occurring in less than 10% of patients, generally following brachytherapy.

Skin or subcutaneous toxicity requiring surgery, pneumonitis, rib fractures, or any grade 3 or greater complications including pain are uncommon after ABPI, and are expected to occur in <10% of patients

Patients will also undergo venipuncture as part of the study. Risks of that procedure include hematoma, swelling, tenderness and inflammation at the site, persistent bleeding, vasovagal response, and rarely thrombosis and infection.

Method of detection, signs and symptoms, and method of treatment will be reported for all detected toxicities

9.0 Ancillary Treatment/Supportive Care

9.1 Skin creams/ointments for the treatment of dermatitis may be used at the discretion of the treating physicians as per standard practice.

10.0 Adverse Event (AE) Reporting and Monitoring

10.1 Definitions

Adverse Event- An untoward or undesirable experience associated with the use of a medical product (i.e. drug, device, biologic) in a patient or research subject.

Serious Adverse Event - Adverse events are classified as serious or non-serious. Serious problems/events can be well defined and include;

- Death
- life threatening adverse experience
- hospitalization
- inpatient, new, or prolonged; disability/incapacity
- persistent or significant birth defect/anomaly

and/or per protocol may be problems/events that in the opinion of the sponsor-investigator may have adversely affected the rights, safety, or welfare of the subjects or others, or substantially compromised the research data.

All adverse events that do not meet any of the criteria for serious, should be regarded as **non-serious adverse events**.

Unanticipated Problems Involving Risks to Subjects or Others (UPIRTSO)- Any unanticipated problem or adverse event that meets the following three criteria:

- Serious: Serious problems or events that results in significant harm, (which may be physical, psychological, financial, social, economic, or legal) or increased risk for the subject or others (including individuals who are not research subjects). These include: (1) death; (2) life threatening adverse experience; (3) hospitalization - inpatient, new, or prolonged; (4) disability/incapacity - persistent or significant; (5) birth defect/anomaly; (6) breach of confidentiality and (7) other problems, events, or new information (i.e. publications, DSMB reports, interim findings, product labeling change) that in the opinion of the

local investigator may adversely affect the rights, safety, or welfare of the subjects or others, or substantially compromise the research data, **AND**

- **Unanticipated:** (i.e. unexpected) problems or events are those that are not already described as potential risks in the protocol, consent document, not listed in the Investigator's Brochure, or not part of an underlying disease. A problem or event is "unanticipated" when it was unforeseeable at the time of its occurrence. A problem or event is "unanticipated" when it occurs at an increased frequency or at an increased severity than expected, **AND**
- **Related:** A problem or event is "related" if it is possibly related to the research procedures.

Preexisting Condition- A preexisting condition is one that is present at the start of the study. A preexisting condition should be recorded as an adverse event if the frequency, intensity, or the character of the condition worsens during the study period. At screening, any clinically significant abnormality should be recorded as a preexisting condition. At the end of the study, any new clinically significant findings/abnormalities that meet the definition of an adverse event must also be recorded and documented as an adverse event.

10.2 Recording Adverse Events

CTCAE term (AE description) and grade: The descriptions and grading scales found in the revised NCI Common Terminology Criteria for Adverse Events (CTCAE) version 4.0 will be utilized for AE reporting. All appropriate treatment areas should have access to a copy of the CTCAE version 4.0. A copy of the CTCAE version 4.0 can be downloaded from the CTEP web site:

10.21 Adverse event monitoring and reporting is a routine part of every clinical trial. First, identify and grade the severity of the event using the CTCAE version 4.0. Next, determine whether the event is expected or unexpected and if the adverse event is related to the medical treatment or procedure. With this information, determine whether the event must be reported as an expedited report (see Section 10.3).

10.22 Assessment of Attribution

When assessing whether an adverse event is related to a medical treatment or procedure, the following attribution categories are utilized:

Definite - The adverse event is clearly related to the agent(s).

Probable - The adverse event is likely related to the agent(s).

Possible - The adverse event may be related to the agent(s).

Unlikely - The adverse event is doubtfully related to the agent(s).

Unrelated - The adverse event is clearly NOT related to the agent(s).

Events determined to be possibly, probably or definitely attributed to a medical treatment suggest there is evidence to indicate a causal relationship between the drug and the adverse event.

10.3 Reporting of Serious Adverse Events and Unanticipated Problems

When an adverse event has been identified, the study team will take appropriated action necessary to protect the study participant and then complete the Study Adverse Event Worksheet and log. The investigator will evaluate the event and determine the necessary follow-up and reporting required.

a. Serious Adverse Events will be reported as part of regular adverse event reporting mechanisms via the data capture system and logged for review reporting.

10.31 Investigator Reporting: Notifying the Mayo IRB:

The IRB requirements reflect the guidance documents released by the Office of Human Research Protections (OHRP), and the Food and Drug Administration (FDA) in early 2007 and are respectively entitled “Guidance on Reviewing and Reporting Unanticipated Problems Involving Risks to Subjects or Others and Adverse Events” and “Guidance for Clinical Investigators, Sponsors, and IRBs: Adverse Event Reporting – Improving Human Subject Protection.”

10.311 According to Mayo IRB Policy any serious adverse event (SAE) which the Principal Investigator has determined to be a UPIRTSO must be reported to the Mayo IRB as soon as possible but no later than 5 working days after the investigator first learns of the problem/event.

10.312 Non-UPIRTSO – the investigator reports problems or events that do NOT meet criteria of an UPIRTSO in summary format at the time of the next continuing review. The investigator monitors the severity and frequency of subsequent non-UPIRTSOs.

Consider the following information to collect when developing any forms for documentation of adverse events.

Example

Information collected on the adverse event worksheet (and entered in the research database):

- Subject's name:
- Medical record number:
- Disease/histology (if applicable):
- The date the adverse event occurred:
- Description of the adverse event:
- Relationship of the adverse event to the research (drug, procedure, or intervention):
- If the adverse event was expected:
- The severity of the adverse event: (use a table to define severity scale 1-5)
- If any intervention was necessary:
- Resolution: (was the incident resolved spontaneously, or after discontinuing treatment)
- Date of Resolution:

The investigator will review all adverse event reports to determine if specific reports need to be made to the IRB and FDA. The investigator will sign and date the adverse event report when it is reviewed. For this protocol, only directly related SAEs/UPIRTSOs will be reported to the IRB.

10.4 Adverse events to be graded at each evaluation and pretreatment symptoms/conditions to be evaluated at baseline per the CTCAE v4.0 grading unless otherwise stated in the table below:

			Each	Grading scale
--	--	--	------	---------------

System Organ Class (SOC)	Adverse event/Symptoms	Baseline	evaluation	(if not CTCAE)
Skin and Subcutaneous tissue disorders	Dermatitis Radiation	X	X	CTCAE
	Telangiectasia	X	X	See 10.1
	Breast Edema = CTCAE Vascular Lymphedema	X	X	CTCAE, BCTOS
	Superficial soft tissue Fibrosis	X	X	CTCAE
	Seroma	X	X	CTCAE
	Skin hyperpigmentation	X	X	CTCAE
	Skin hypopigmentation	X	X	CTCAE
Infections and infestations	Breast infection	X	X	CTCAE
Respiratory, thoracic and mediastinal disorders	Pneumonitis	X	X	CTCAE
General disorders and administration site conditions	Non-cardiac chest pain	X	X	CTCAE

BCTOS = Breast Cancer Treatment Outcomes Scale

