In the Electron IntraOperative Therapy (ELIOT) phase III trial, patients aged 48-75 years with invasive tumors ≤ 2.5 cm were randomized to 21Gy in 1 fractions to the tumor bed using 6-9MEV electrons prescribed to the 90% isodose line (n=651) or whole breast EBRT to 50Gy followed by a 10Gy boost.²⁸ 88.4% of patients on the study received endocrine therapy and 21.5% had chemotherapy. The study was designed with an assumed 5-year local recurrence rate of 3% in the EBRT group and equivalence of the two groups if the 5-year local recurrence rate in the ELIOT group did not exceed 7.5%. The 5-year event rate for IBTR was 4.4% (95% CI 2.7-6.1) in the ELIOT group, which was significantly higher compared to the 0.4% (0.0-1.0) rate in the conventional group, p=0.0001. The hazard ratio for the development of IBTR was 9.3 [95% CI 3.3-26.3]. The rate of IBTR in the intraoperative radiotherapy group, however, was within the prespecified equivalence margin. The 5-year IBTR exceeded 10% in patients with tumors > 2 cm, patients with four or more positive lymph nodes, grade 3 tumors, ER negative tumors, and triple negative tumors. In multivariable analysis, tumor size greater than 2cm (HR 2.24, 95% CI 1.03-4.87), the presence of four or more positive lymph nodes (2.61, 0.91-7.50), grade 3 (2.18, 1.00-4.79), and triple-negative subtype (2.40, 0.94-6.10) were associated with elevated risk of IBTR. The 5-year occurrence of IBTR was 1.5% in the 452 women who did not have one of these unfavorable characteristics. The development of distant metastasis and overall survival at 5 years did not differ significantly between the two groups. There was significantly less erythema, dryness, hyperpigmentation, and pruritus in the ELIOT group, but a higher occurrence of fat necrosis.

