prescribed in NSABP B-39/RTOG 0413 as well as the Canadian Accelerated Partial Breast Irradiation Using Three-Dimensional Conformal External Beam Radiation Therapy (RAPID) randomized trials. Olivotto et al. recently reported the interim cosmetic and toxicity results from the latter study which compared 3D-conformal APBI to whole breast irradiation (WBI). 82% of patients in the WBI arm received 42.5Gy in 16 fractions, and just 21% of patients received a boost. At 3 years, 29% of patients in the APBI arm had fair or poor cosmesis compared to 19% at baseline, an absolute difference of 10%. In the WBI arm, the rate of fair or poor cosmesis at 3 years was 17%, the same rate as at baseline. Telangiectasia and breast induration were also significantly more common with external beam APBI ($p<0.001$), as was fat necrosis ($p=0.01$).⁴⁷ Other institutions have also noted adverse toxicity with similar regimens.^{22,48}

There are likely several reasons for the higher than expected adverse cosmesis seen in the RAPID trial that may be also relevant to the increased complications seen with brachytherapy in population based analyses. These considerations have been taken into account in the development of the brachytherapy, external beam photon and proton fractionation regimens of this study. First, the dose of 38.5Gy in 10 fractions given twice daily was too high. The RAPID trial investigators recognized that this prescription had a higher biologic equivalence than the whole breast regimens used in the study, but they hypothesized that the reduced volume of APBI would make up for this difference. Indeed, using an α/β ratio of 3.5 for late effects, the 3.85Gy x 10 fraction regimen translates into 51.5Gy in 2 Gy fractions, higher than the 2Gy fraction equivalent dose of 42.5Gy delivered in 16 fractions (47.7Gy₂) which was received by the majority of patients in the WBI control arm of the study.

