2.0 Goals

2.1 Primary:

- 2.11 To evaluate the rate of adverse cosmesis (defined as fair or poor cosmesis) with accelerated 3 fraction APBI at 3 years, compared to baseline.

2.2 Secondary:

- 2.21 To evaluate the acute and late toxicities of accelerated 3 fraction APBI
- 2.22 To evaluate local disease control of accelerated 3 fraction APBI.
- 2.23 To assess the rate of patient reported adverse cosmesis at 2 years, compared to baseline

- 2.23 To assess quality of life and other patient reported outcomes following accelerated 3 fraction APBI
- 2.24 To compare the local control, acute and late toxicities, cosmesis, quality of life and other patient reported outcomes between the three radiation therapy techniques (3D-CRT, proton, brachytherapy).
- 2.24 To evaluate clinical features, dose-volume parameters, and genetic variants associated with fair and poor cosmetic outcome

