11.3 Cosmesis evaluation and Patient Reported Outcomes

11.31 Digital photographs should be performed according to the schedule outlined in section 4.0 and should include three poses: from the front with hands on hips and both lateral views. Recommended framing should go from the sternal notch to the umbilicus. If possible, patients should be photographed against a solid colored background.

11.32 The Harvard Cosmesis Scale will be used to score cosmesis according to the schedule outlined in section 4.0. The patients will be assessed as one of the following:

- Excellent: treated breast nearly identical to untreated breast
- Good: Treated breast slightly different than untreated (minimal but identifiable effects of the treated breast)

- Fair: Treated breast clearly different from untreated but not seriously distorted (significant radiation effects readily observable)
- Poor: Treated breast seriously distorted (severe sequelae of breast tissue secondary to radiation effects)

A modified version of the Harvard Cosmesis Scale will also be used for patient reported assessment of cosmesis.

11.33 The Breast Cancer Treatment Outcome Scale (BCTOS) is a self-report instrument that has high reliability and validity and will be used for evaluating patient-rated cosmesis according to the schedule outlined in section 4.0.

11.34 Patient-Reported Outcomes Version of the Common Terminology Criteria for Adverse Events (PRO-CTCAE) will be used for patient self-reporting of toxicities in the CTCAE.

11.35 Other Patient Reported Outcome questions (fatigue, pain, arm function etc.) included in the appendix.

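### The solicited toxicity list in 10.4 omits fat necrosis and rib fracture and has no clinician-graded row for breast pain, so these effects are likely to be recorded less completely than the listed ones

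*Combined protocol and SAP*

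**What the plan says.** A secondary goal (2.21) is "To evaluate the acute and late toxicities of accelerated 3 fraction APBI". Section 10.4 sets out the "Adverse events to be graded at each evaluation and pretreatment symptoms/conditions to be evaluated at baseline per the CTCAE v4.0 grading". Its ten terms are radiation dermatitis, telangiectasia, breast edema, superficial soft tissue fibrosis, seroma, hyperpigmentation, hypopigmentation, breast infection, pneumonitis and non-cardiac chest pain.

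Elsewhere the protocol names effects that have no row:

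- **Fat necrosis.** On the randomized comparison of 3D-conformal APBI with whole-breast irradiation, section 1.3.2 says "Telangiectasia and breast induration were also significantly more common with external beam APBI" (p<0.001), and adds "as was fat necrosis" (p=0.01). In section 1.2, the intraoperative electron trial showed fewer skin effects "but a higher occurrence of fat necrosis".
- **Breast pain.** Section 8.2: "Mild swelling of the breast or mild breast pain are also likely side effects of treatment".
- **Rib fracture.** Section 8.2: "Skin or subcutaneous toxicity requiring surgery, pneumonitis, rib fractures, or any grade 3 or greater complications including pain are uncommon after ABPI", with an expected frequency below 10%.

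Section 18.1 requires the solicited adverse event form after radiation and at observation visits. The Adverse Events Other and Adverse Events: Late forms are marked for use only where they apply. Section 11.34 plans PRO-CTCAE, which "will be used for patient self-reporting of toxicities in the CTCAE", and 11.35 adds patient questions that include pain.

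**The concern.** A late-toxicity rate is only as complete as its collection. A listed event is looked for and graded in every woman at every evaluation. An unlisted event is recorded only if someone notices it and decides to open another form. If the two kinds of event then appear in one table, the unlisted ones will tend to look rarer than they are.

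Fat necrosis is the clearest case. The protocol's own benchmark trial found three late toxicities more frequent with external beam APBI, and the list picks up two. In the intraoperative electron trial, several skin effects favored partial-breast treatment while fat necrosis went the other way. A list weighted toward skin effects could therefore look favorable while missing an effect that has run against APBI.

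At stake are the description of late toxicity under objective 2.21 and the comparison of the three techniques (goal 2.24, section 16.7). Spontaneous reporting may also differ by clinician or technique. Section 1.3.2 further expects late toxicity to fall because daily treatment allows more complete repair, and that expectation is best examined with even ascertainment of the known late effects.

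**Working it through.** The plan states no figure on this point, so the check sets its sections side by side.

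**Step 1. Compare the effects named with the 10.4 rows and other prompted routes.**

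| Effect | Where named | Row in 10.4 | Other prompted route visible |
|---|---|---|---|
| Telangiectasia | 1.3.2 (p<0.001), 8.2 | Yes, with its own scale in 10.41 | Not needed |
| Induration (fibrosis) | 1.3.2 (p<0.001), 8.2 | Yes, as superficial soft tissue fibrosis | Not needed |
| Fat necrosis | 1.3.2 (p=0.01), 1.2 | No | None |
| Rib fracture | 8.2; ribs are also within the chest wall dose limit in 7.12 | No | None; non-cardiac chest pain is at most a symptom |
| Breast pain | 8.2 | No; the only pain term is non-cardiac chest pain | Yes: 11.34 and 11.35 |

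Counts: 2 of the 3 late toxicities singled out in 1.3.2 are solicited. Of fat necrosis, rib fracture and breast pain, 0 of 3 are among the ten terms.

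**Step 2. Trace how an unlisted event is recorded.** Under 18.1 it goes on Adverse Events Other or Adverse Events: Late, neither of which is mandatory at a visit. Section 8.2 asks for the method of detection and treatment of toxicities, but only for those already detected. Section 16.62 tabulates every type of late adverse event, so a recorded case is counted. The gap lies in ascertainment, not in analysis.

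**Step 3. Check baseline.** Section 6.22 requires baseline symptoms to be graded by reference to section 10, so a term without a row has no required baseline grade. Section 10.1 asks for clinically significant abnormalities at screening to be recorded as preexisting, which gives partial cover. For pain, section 4.0 schedules the patient-reported assessment at baseline and at later evaluations, and 16.63 analyzes change from baseline.

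**Step 4. Size.** The documents give p-values for fat necrosis but no rate, and nothing on how completely unprompted events are recorded. A shortfall in events or percentage points cannot be derived.

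**The case against.** The best case against the point is that this is a checklist matter in a secondary endpoint. All adverse events remain reportable, a history and breast examination take place at the scheduled evaluations, and most effects named in 8.2 are solicited. That is fair, and it is why the point is minor. It does not remove the difference between asking and not asking.

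A reader might also infer stronger conclusions that the documents do not support:

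- **That the list misses the effects most at issue.** Telangiectasia and induration carry the smaller p-value in 1.3.2, and both are solicited, as is breast edema. Fat necrosis is one of three, and it appears in the background rather than among the expected events in 8.2.
- **That all three effects reach the database only through the Other form.** There is also an Adverse Events: Late form, and pain has patient-reported routes. Section 18.1 also lists a Breast/Chest Wall Radiotherapy Questionnaire. The questionnaire items are not in the available text, so a breast-specific pain item can be neither confirmed nor excluded.
- **That surgical pain cannot be separated from later pain.** Patient-reported pain has a baseline.
- **That the pooling check in 16.43 or the stopping rules in 16.92 are weakened.** These use grade 3 toxicity and grade 3 or higher events respectively, which are less easily missed; nothing shows that such events would go unrecorded.
- **That the rates could not be compared with the benchmark trial because that trial solicited fat necrosis.** The documents do not say how it collected the event.

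**Conclusion.** The point holds in a limited form. Fat necrosis and rib fracture have no visible prompted route, so their reported rates are likely to be too low relative to the ten listed effects. Breast pain lacks only a clinician-graded term. Fat necrosis matters most, because the protocol itself reports it as significantly more frequent with external beam APBI.

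This is a cheap improvement and does not threaten the primary endpoint or any decision rule. The direction of the shortfall rests on three assumptions: that prompted events are recorded more completely than unprompted ones, that the solicited form mirrors the 10.4 table, and that the unseen questionnaire items do not ask about fat necrosis or rib fracture. Any percentage put on the shortfall would be a guess.

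**What to change.** Add three rows to 10.4, graded at baseline and at each evaluation:

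- **Fat necrosis**, when clinically evident or seen on imaging done for clinical reasons. Define a simple scale in 10.41, beside the existing telangiectasia scale: none, present without symptoms, symptomatic, requiring intervention.
- **Rib fracture**, when clinically detected.
- **Breast pain**, by CTCAE.

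Carry the rows onto the solicited form and report them in the 16.61 and 16.62 tables. If the sponsor prefers not to add rows, the protocol should at least state how each effect is ascertained, so that readers can interpret its rate.

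The cost is a slightly longer form. Section 4.0 already schedules the breast examination and toxicity assessment together, so no visit, staff or imaging is added. Reported toxicity will probably rise somewhat, which the report should attribute to prompting. One limit remains: follow-up mammograms are left to clinical indication, so fat necrosis without symptoms will still be captured incompletely, and the report should say so.
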